5.5.7.2. Laboratory Measurements

Descriptive statistics for continuous hematology, clinical chemistry, urinalysis, and coagulation laboratory measurements will be presented by time point. Summary statistics for each lab parameter and time point as well as the change from Baseline to the time point will be displayed. For each numeric laboratory parameter, box plots of values over time will be generated. A shift table will compare N (%) of low, normal, and high status of the lab values at Baseline to their worst value post-Baseline through Week 96. A table summarizing the frequency and percent of subjects meeting the predefined markedly abnormal criteria at each visit will be presented. The predefined markedly abnormal criteria are defined below in Tables 3-1, 3-2, and 3-3. All laboratory values will be displayed in a data listing.

Table 3-1 Predefined Markedly Abnormal Hematology Laboratory Values

Test	Unit	Markedly Abnormal Criteria
Hematocrit	1	< LLN
Hemoglobin	g/L (or mmol/L)	< LLN
Red blood cell count	T/L	< LLN
White blood cell count	count/L	$>1.5 \times ULN \text{ or } < LLN$
Platelet count	10^3/L	< 150 or < 200 with a decrease of at least 100
Basophils (abs)	count/L	> ULN or < LLN
Eosinophils (abs)	count/L	> 1.5xULN or < LLN
Lymphocytes (abs)	count/L	< LLN
Monocytes (abs)	count/L	< LLN
Neutrophils (abs)	count/L	>1.5 × ULN or < 1000

ULN = upper limit of normal

LLN = lower limit of normal

abs = absolute

Table 3-2 Predefined Markedly Abnormal Chemistry Laboratory Values

		Predefined	Change	
Test	Unit	Decrease	Increase	Markedly Abnormal Criteria
Fasting blood glucose*	mmol/L	3.1	3.2	
Urea (BUN)	mmol/L			Value >1.5 × Baseline Value AND > ULN
Creatinine	μmol/L		35	Value >1.5 × ULN
Sodium	mmol/L	8	8	
Potassium	mmol/L	1.1	1.0	Value >5.5 mmol/L or < 3 mmol/L
Chloride	mmol/L	9	8	
Uric acid	μmol/L			>1 × ULN
Calcium#	mmol/L	0.30	0.30	
Total cholesterol	mmol/L		1.73	
AST (SGOT)	U/L			Value ≥3 × Baseline Value
ALT (SGPT)	U/L			Value ≥2 × Baseline Value
Gamma GT (GGT)	U/L			Value >3 × Baseline Value OR > ULN
Alkaline phosphatase	U/L			Value >1.5 × ULN
Total protein@	g/L	11	10	
Albumin	g/dL	1 g/dL decrease or	1 g/dL increase	Value < LLN or > ULN
Total bilirubin ^{&}	μmol/L		10	Value >1.5 × ULN
LDH	U/L			Value ≥2 × Baseline Value
Creatine phosphokinase	U/L			Value ≥2 × Baseline Value
Triglycerides	mmol/L	_	2.88	
Cystatin C	mg/L			>ULN

^{*}Convert to SI unit by multiplying mg/dL value by 0.0555; *multiply mg/dL value by 0.25; @multiply g/dL value by 10; &multiply mg/dL value by 17.1.

LLN = lower limit of normal

ULN = upper limit of normal

TEMA = treatment-emergent markedly abnormal

Table 3-3 Predefined Marked	v Abnormal Urinalysi	s Laboratory Values
-----------------------------	----------------------	---------------------

	Predefined Change		
Test	Decrease	Increase	Markedly Abnormal Criteria
Protein in urine			>1+
KIM-1*			> ULN

^{*} Adult normal ranges provided by the laboratory will be used for all subjects as no pediatric ranges are available.

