8.5. Patient Withdrawal Criteria

Any patient can decide to withdraw from study participation at any time for any reason. In addition, the study Sponsor may decide to stop the study participation of any patient as deemed necessary. The Investigator may also stop the study participation of any patient at any time. Reasons for study withdrawal include but are not limited to:

- The patient was erroneously included in the study (i.e., was found to have not met the eligibility criteria).
- The patient experiences an intolerable or unacceptable AE.
- The patient is unable to comply with the requirements of the protocol.
- The patient participates in another investigational study without the prior written authorization of the Sponsor.

The Investigator or study staff will document the reason(s) for treatment discontinuation on the case report form (CRF).

Patients who received at least 1 dose of IP who discontinue from treatment within 4 weeks after a functional assessment visit will be asked to return for an End of Study visit within 4 weeks of their last visit. Patients who received at least one (1) dose of IP who discontinue treatment more than 4 weeks after a functional assessment visit will be asked to complete all Early Termination (Week 96) assessments within 30 days of discontinuation and a subsequent End of Study visit within 4 weeks of the Early Termination (ET) visit.

Following Week 96, patients may continue to receive eteplirsen for up to an additional 48 weeks and be followed as described in the Safety Extension portion of Section 2, Table 3 (Safety Extension Schedule of Events). They may receive weekly infusions of eteplirsen at the same dose, with continuous monitoring of adverse events and concomitant medications, while undergoing physical examination and safety laboratory assessments every 24 weeks. If patients discontinue eteplirsen during the Safety Extension, they will be asked to return for an End of Study visit 4 weeks after their final dose.

Patients who discontinue eteplirsen dosing in the Safety Extension Period in order to transition onto commercial drug or into a separate eteplirsen study do not require an End of Study visit.

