1. INTRODUCTION

This analysis plan summarizes the planned analyses and presentation of the safety and efficacy data from the Sarepta Therapeutics, Inc. Protocol 4658-204: "An Open-Label, Multi-Center Study to Evaluate the Safety and Tolerability of eteplirsen in Patients with Advanced Stage Duchenne Muscular Dystrophy".

The investigational product is eteplirsen injection. Eteplirsen 30 mg/kg will be administered as an intravenous (IV) infusion over approximately 35 to 60 minutes, or approximately 5 mL/min, once a week for up to 96 weeks, followed by a safety extension (not to exceed 48 weeks), until the product is commercially available or until patients can transition into another eteplirsen trial.

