- Screening ECG, Holter ECG, and ECHO may be performed at any time during the Screening period; however results must be available on Day 1, prior to dosing.
- g In the event of early termination prior to Week 96, the Week 96 assessments should be completed as the Early Termination Visit.
- ^h End of Study visit should occur within 4 weeks after last dose

Version 1.0 (20 April 2017) Page 11 of 40

Study Period					7	Гreatm	ent Per	riod					Safety Extension	End of Study ^h
Week	52	56	60	64	68	72	76	80	84	88	92	96/ET ^g	See Table 2	4 weeks after last infusion (as applicable)
Informed Consent														
Inclusion/Exclusion														
Medical History														
Full Physical Exam						X						X		X
Brief Physical Exam														
Vital Signs ^a	X	X	X	X	X	X	X	X	X	X	X	X		X
Weight	X	X	X	X	X	X	X	X	X	X	X	X		X
Safety Lab Assessments ^b						X						X		X
CCI														
Whole Blood (Genotyping/CCI) ^c														
Height and Ulnar Length						X						X		
CCI														
CCI														
ECG						X						X		
Holter ECG												X		
ЕСНО						X						X		
Study Drug Infusion							Once	Weekl	y					

Version 1.0 (20 April 2017)

Page 12 of 40

Study Period					7	[reatm	ent Per	iod				Safety Extension	End of Study ^h
Week	52	56	56 60 64 68 72 76 80 84 88 92 96/ET ^g last infusio					4 weeks after last infusion (as applicable)					
Conmed/Therapy		Continuous											
AE Assessment								С	ontinuo	us			

Footnotes for Table 1 Schedule of Events: Week 52 through End of Study

Functional assessments, \overline{CCI} , ECG, Holter ECG, and ECHO have a \pm 2 weeks window

- ^a For infusion visits, vital signs are to be collected within approximately 30 minutes prior to infusion and approximately 5, 30, and 60 minutes after the end of the infusion. If the patient has not experienced an infusion reaction after the first year of treatment, vital signs may be collected only 30 minutes after the end of the infusion.
- ^b Blood samples for the safety laboratory assessments must be obtained within 2 weeks prior to the Baseline/Week 1 visit, and results must be available prior to dosing at Baseline/Week 1. If more than 2 weeks have elapsed since the collection of blood samples for the Screening safety laboratory assessments, it must be repeated. If less than 2 weeks have elapsed since the collection of blood samples for the Screening safety laboratory assessments, additional safety laboratory assessments do not need to be performed.

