- ^c Patients may start dosing based on local genotyping results provided that these results fulfill the required inclusion criteria; however, all patients must undergo genetic testing to confirm the exon 51 skippable mutation CCI.
- Screening ECG, Holter ECG, and ECHO may be performed at any time during the Screening period; however results must be available on Day 1, prior to dosing.
- g In the event of early termination prior to Week 96, the Week 96 assessments should be completed as the Early Termination visit.
- ^h End of Study visit should occur within 4 weeks after last dose

Version 1.0 (20 April 2017) Page 13 of 40

Table 2 Schedule of Events - Safety Extension Period

Study Period	Safety Extension Period (Starting at Week 97 and continuing until the product is commercially available or until patients can transition into a separate eteplirsen study)						
Week	120	144					
Full Physical Exam	X	X					
Vital Signs ^a	Wee	Weekly					
Weight	Every 4	Every 4 Weeks					
Safety Lab Assessments	X	X					
CCI							
CCI							
ECG	X	X					
ЕСНО	X	X					
Study Drug Infusion	Once V	Once Weekly					
Conmed/Therapy	Conti	Continuous					
AE Assessment	Conti	Continuous					

Functional assessments, CCI, ECG, Holter ECG, and ECHO have a ±2 weeks window

Version 1.0 (20 April 2017) Page 14 of 40

^a For infusion visits during the Safety Extension Period, vital signs are to be collected within approximately 30 minutes prior to infusion and approximately 5, 30, and 60 minutes after the end of the infusion. If the patient has not experienced an infusion reaction in the past year of treatment, vital signs may be collected only 30 minutes after the end of the infusion.

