5.4.6 Definitions and Terminology

Study Day

Study day will be defined as Event Date – Study Day 1 + 1

Study Day 1

Day 1 is defined as the date of first dose of eteplirsen at the Week 1 visit during the 4658-204 Study.

Days on Study

Days on Study is the number of days from Study Day 1 to the date of study completion or early termination as recorded on the END OF STUDY VISIT CRF.

Days on Study Drug

Days on Study Drug is the number of days from the date of first dose to the date of the last dose of the specific study medication as recorded on the STUDY DRUG ADMINISTRATION CRF.

Planned Number of Infusions

The planned number of infusions will be based on the subject's last local site visit. The subject will be expected to receive an infusion once weekly up until their last local site

visit. If a subjects completes 100 local site visits and then completes or discontinues the study the planned number of infusions will be 100.

Treatment Group

All subjects received 30 mg/kg weekly of eteplirsen and will be analyzed in the same group.

Time Since DMD Diagnosis

The time since DMD diagnosis, in months, will be calculated as Month and Year of first dose – Month and Year of diagnosis

Treatment-Emergent Adverse Event

An AE is considered treatment-emergent if it occurs on or after the initiation of the first dose of eteplirsen and within 28 days of last dose.

Treatment Related Adverse Event

A treatment-related AE is any adverse event reported on the CRF that is marked as definitely, probably or possibly related to study drug. Additionally, it is assumed that an AE without a relationship is treatment-related.

Treatment-Emergent Laboratory Abnormality

[figure not shown]
A treatment-emergent laboratory abnormality is defined as any laboratory abnormality (as defined in section 5.5.7.2) that occurs following the initiation of eteplirsen which was not present at Baseline.

Prior Medication

A prior medication is any medication taken prior to the first study drug administration.

Concomitant Medication

A concomitant medication is any medication that is taken on or after the first study drug administration.

Final Analyses

An analysis will be performed once all subjects complete their End of Study visit and the resulting clinical database has been cleaned, quality checked and locked through the data cut.

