5.5.7.3. Vital Signs

Vital sign parameters will be presented by time point, summarizing the actual values and change from Baseline to each on-treatment time point using descriptive statistics. A table summarizing the frequency and percent of subjects meeting the predefined markedly abnormal criteria at each visit will be presented. The predefined markedly abnormal criteria are defined below in Table 4. Vital signs data will be presented in the data listings.

Table 4 Predefined Markedly Abnormal Vital Sign Values

Variable	Units	Markedly Abnormal Criteria Lower limit	Markedly Abnormal Criteria Upper limit
Systolic blood pressure	mm Hg	<80	>130
Diastolic blood pressure	mm Hg	<40	>90
Pulse Rate	beats/min	<50	>130
Temperature	°C		≥40

5.5.7.4. 12-Lead ECGs

Electrocardiogram (ECG) parameters will be presented by time point, summarizing the actual values and change from Baseline to each on-treatment time point using descriptive statistics. A shift table will compare N (%) of ECG status at Baseline to the worst reported value through Week 96. A table summarizing the frequency and percent of subjects meeting the predefined markedly abnormal criteria at each visit will be presented. The predefined markedly abnormal criteria are defined below in Table 5. ECG data will be provided in a data listing.

Table 5 Predefined Markedly Abnormal Electrocardiogram Values

Variable	Units	Lower limit of normal	Upper limit of normal	Age Group (yrs)	Markedly Abnormal Criteria
Heart Rate	beats/min	50	120		
QTcF Interval	msec			All	Screening Visit >450
				<12	>480
				≥12	>500
				All	<320
					Increase >60
QRS Interval	msec			<12	IVCD or any QRS conduction disturbance
					with a QRS >110ms
				≥12	IVCD or any QRS conduction disturbance
					with a QRS >120ms
PR Interval	msec			<12	>190
				≥12	>220

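### The lab and ECG shift tables, the only per-patient worst-value summaries planned, stop at Week 96 although safety data may be collected for up to 48 more weeks of dosing

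*SAP*

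**What the plan says.** The laboratory shift table in SAP 5.5.7.2 classifies results as low, normal or high and compares "values at Baseline to their worst value post-Baseline through Week 96". SAP 5.5.7.4 sets the same limit for ECGs: "A shift table will compare N (%) of ECG status at Baseline to the worst reported value through Week 96".

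Treatment and assessment can go further. Protocol 8.5 states: "Following Week 96, patients may continue to receive eteplirsen for up to an additional 48 weeks". It describes those patients as "undergoing physical examination and safety laboratory assessments every 24 weeks". The extension schedule (Protocol Table 3, SAP Table 2) marks safety labs and ECG at Weeks 120 and 144. The main schedule also marks safety labs, but no ECG, at the End of Study visit. On timing, SAP 5.4.6 says: "An analysis will be performed once all subjects complete their End of Study visit". No interim analysis is planned (Protocol 13.10).

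Other parts of the plan carry no Week 96 limit:

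- the protocol's safety endpoint, the incidence of laboratory and ECG abnormalities (7.3.1);
- the SAP's definition of a treatment-emergent laboratory abnormality (5.4.6);
- the TEAE window, which runs to 28 days after the last dose (SAP 4.4.5 and 5.4.6);
- the ECG shift table as the protocol describes it (13.8.2.4).

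SAP Section 6 declares one change from the protocol, which concerns Holter data. It does not mention the ECG cut-off.

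**The concern.** Safety is the primary objective, and the endpoint is an incidence: how many patients developed an abnormality. For labs and ECGs, the shift table is the only planned output that reduces each patient's record to one worst result and so counts each patient once. Ending it at Week 96 leaves out data that will be in the locked database when the single analysis is run, and those data come from the patients with the longest exposure.

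A patient whose first high creatinine or first abnormal ECG occurs at Week 120 or 144 does not count as shifted in that table. An adverse event arising from the same finding would be counted, because the AE window has no such limit. The lab and AE summaries therefore answer the safety question over different periods, and the SAP gives no reason for the difference.

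**Working it through.** The plan states no figure to reproduce here. The check is a count of scheduled time points, a comparison of outputs, and an illustration under stated assumptions.

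**Step 1: scheduled post-Baseline time points (Protocol Tables 2 and 3; SAP Tables 1 and 2)**

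- Labs through Week 96: Weeks 4, 8, 12, 24, 36, 48, 72, 96 = 8. After: Weeks 120, 144 and End of Study = 3. Share outside the table: 3/(8+3) = 27%.
- ECG through Week 96: Weeks 12, 24, 36, 48, 72, 96 = 6. After: Weeks 120 and 144 = 2. Share outside: 2/(6+2) = 25%.
- Dosing weeks: 48/(96+48) = 33%.

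These shares apply to a patient who completes all 48 extension weeks and, for labs, attends End of Study.

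**Step 2: what the other outputs show after Week 96**

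- The by-time-point summaries of values and changes, the lab box plots, the by-visit markedly abnormal tables and the listings have no cut-off, so the late values are reported.
- The by-visit counts cannot be added into a patient count, because one patient can appear at several visits.
- The markedly abnormal criteria are not the low/normal/high classes. For creatinine, SAP Table 3-2 gives a rise of 35 µmol/L or a value above 1.5 × ULN. A first value just above ULN at Week 120 can meet neither, and it is then categorised in no table.
- SAP Tables 3-1 to 3-3 cover hematology, chemistry and urinalysis. They give no criteria for prothrombin time, INR or aPTT, which Protocol 10.3.3 collects. For these tests the shift table is the only categorical summary, and after Week 96 there is none, although SAP 5.5.7.1.1 lists coagulopathy as an AE of special interest.

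**Step 3: possible size in patients**

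Assumptions not in the documents: all 20 patients are followed through Week 144 and End of Study, visits are independent, and the chance p of an abnormal result on a given parameter is the same at every visit. The chance of at least one abnormal result in k visits is 1 − (1 − p)^k. Patients first abnormal after Week 96 number 20 × [(1 − p)^8 − (1 − p)^11] for labs and 20 × [(1 − p)^6 − (1 − p)^8] for ECG.

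| p | Labs to Wk 96 | Labs, all | First abnormal later, of 20 | ECG to Wk 96 | ECG, all | First abnormal later, of 20 |
|---|---|---|---|---|---|---|
| 1% | 7.7% | 10.5% | 0.55 | 5.9% | 7.7% | 0.37 |
| 2% | 14.9% | 19.9% | 1.00 | 11.4% | 14.9% | 0.70 |
| 5% | 33.7% | 43.1% | 1.89 | 26.5% | 33.7% | 1.43 |
| 10% | 57.0% | 68.6% | 2.33 | 46.9% | 57.0% | 2.02 |

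Under these assumptions, between less than one and just over two patients per parameter are affected. Shorter or incomplete extension follow-up lowers every figure in the two columns of later cases.

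**The case against.** The strongest defence is that Week 96 is the planned treatment period. Protocol 7.4 regards 96 weeks as adequate for safety follow-up and presents the extension as a way to continue treatment until commercial supply or transfer. Disposition is also summarised through 96 weeks (SAP 5.5.1). A fixed window keeps follow-up comparable between patients. The protocol promises no lab shift table at all, so the SAP adds one. With about 20 patients, a new abnormality at Week 120 would be seen in the by-visit output or listings, and one that changed medical care would also be an AE (Protocol 11.2.1). All of this stands. It is a good reason to keep the Week 96 tables, but it does not supply a whole-study patient count.

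A reader might infer that the plan hides late or cumulative toxicity. The documents do not support that. Late values are displayed, and the by-visit changes and box plots show timing better than a worst-value table does. A table labelled as running to Week 96 makes no claim about later weeks, so the fixed window is not in itself a bias.

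A reader might also infer that about a quarter of affected patients are missed. In the illustration, 17% to 26% (labs) and 18% to 24% (ECG) of patients ever abnormal are first abnormal after Week 96. Those figures need full extension follow-up and a constant per-visit risk, and neither is in the documents. The extension may end early, and patients leaving it for commercial drug or another eteplirsen study need no End of Study visit (Protocol 8.5). The real loss could be close to zero.

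**Conclusion.** The point holds as a gap in the summary tables. Data that may be collected after Week 96, and that are available at the only analysis, enter no per-patient worst-value summary. For low/normal/high lab status, including all coagulation tests, they enter no categorical table.

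The omission is at most 3 of 11 lab and 2 of 8 ECG scheduled time points per patient. The End of Study part applies to labs only. It is also uncertain for patients who stop before Week 96: their End of Study lab may precede Week 96 on the calendar, values are assigned by nominal eCRF page (SAP 5.4.5), and the SAP does not say on which side of the cut-off that visit falls. How many patients are affected depends on extension uptake and length, which the documents do not give.

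For ECGs there is also a documentation gap: the cut-off narrows a table the protocol describes without a limit, and SAP Section 6 does not say so. This is an inexpensive improvement to the primary safety summary. It does not invalidate the planned analysis.

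**What to change.** Keep both Week 96 shift tables. Beside them, add the same two tables using the worst of all post-Baseline values, scheduled and unscheduled. Include Weeks 120 and 144 and, for labs, the End of Study visit whenever it occurs. Report how many patients contribute data after Week 96 and their length of follow-up. List the Week 96 limit on the ECG shift table in SAP Section 6.

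It would be natural to borrow the AE window of 28 days after the last dose, but that can drop End of Study labs. Under Protocol 8.5, some early stoppers have the Early Termination visit up to 30 days after discontinuation and End of Study up to 4 weeks after that: 30 + 28 = 58 days. Taking all post-Baseline values avoids this.

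The cost is a few sentences in the SAP and a second run of two tables. The drawback is that follow-up differs between patients in the added tables, which is why the fixed-window versions should stay and follow-up length should be shown.

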- 3. Previous treatment with drisapersen (PRO051) within the last 6 months. Participation in any other DMD interventional clinical study within 12 weeks of study drug administration, or use of the shock training system or "STS," or planned use during this study. Concurrent participation in an interventional clinical study or observational trial is not permitted.
- 4. Major change in physiotherapy regimen within the past 3 months or expected change over the study period.
- 5. Major surgery within 3 months of study drug administration or planned major surgery for any time during this study.
- 6. Presence of other clinically significant illness including significant cardiac, pulmonary, hepatic, renal, hematologic, immunologic, behavioral disease or malignancy.

NAME OF COMPANY

Sarepta Therapeutics Inc.

[name] [contact]

NAME OF FINISHED PRODUCT

Eteplirsen Injection

NAME OF ACTIVE INGREDIENT

Eteplirsen

- 7. Systemic use of any aminoglycoside antibiotic within 12 weeks of study drug administration or anticipated need for use of an aminoglycoside antibiotic or statin during the study.
- 8.
- 9. Must not require antiarrhythmic and/or antidiuretic therapy for heart failure. Patients are allowed to take other medication including angiotensin-converting enzyme (ACE) inhibitors, angiotensin receptor blocking agents (ARBs), β blockers or potassium, provided they have been on a stable dose for 24 weeks prior to study drug administration and the dose is expected to remain constant throughout the study.
- 10. **cc**
- 11. Prior or ongoing medical condition that could, in the Investigator's opinion, adversely affect the safety of the patient, make it unlikely that the course of treatment would be completed, or impair the assessment of study results.

DOSE/ROUTE/REGIMEN (TEST ARTICLE):

Eteplirsen 30 mg/kg will be administered as an IV infusion over approximately 35-60 minutes once a week for up to 96 weeks, followed by a safety extension (not to exceed 48 weeks), until the product is commercially available or until patients can transition into a separate eteplirsen study.

REFERENCE TREATMENT:

None

[figure not shown]
CRITERIA FOR EVALUATION:

Safety Endpoints

The incidence of the following:

- Adverse events
- Clinical laboratory abnormalities
- Abnormalities in vital signs and physical examinations
- Abnormalities on ECGs and ECHOs

Exploratory Endpoints:

NAME OF COMPANY

Sarepta Therapeutics Inc. [name]

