7.3. Study Endpoints

7.3.1. Safety Endpoints

Incidence of:

- Adverse events
- Clinical laboratory abnormalities
- Abnormalities in vital signs and physical examinations
- Abnormalities on electrocardiograms (ECGs) and echocardiograms (ECHO)

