5.5.7.5. Echocardiograms

The actual value and change from Baseline to each on-treatment time point will be summarized for each ECHO parameter. A table summarizing the frequency and percent of subjects meeting the predefined markedly abnormal criteria at each visit will be presented. The predefined markedly abnormal criteria are defined below in Table 6. ECHO parameters will be listed by subject in a data listing.

Table 6 Predefined Markedly Abnormal Echocardiography Values

Variable	Units	Markedly Abnormal Criteria
LVEF	%	<55%
Fractional Shortening	%	<44%

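### The SAP counts subjects meeting its markedly abnormal criteria only visit by visit, so the planned tables do not show how many subjects ever, or newly, met a criterion; the gap is complete for vital signs and ECHO and partial for ECG and laboratory tests

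*SAP*

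**What the plan says.** The protocol introduces the safety endpoints as "The incidence of the following" (Synopsis; likewise 7.3.1 and 13.8.1). It then names adverse events and abnormalities in laboratory tests, vital signs, physical examinations, ECGs and ECHOs. It sets no period and no rule for abnormalities already present at Baseline.

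The SAP sets numerical thresholds in Tables 3-1 to 3-3 (laboratory), 4 (vital signs), 5 (ECG) and 6 (ECHO). One sentence, used for all four data types, says how they are counted: "A table summarizing the frequency and percent of subjects meeting the predefined markedly abnormal criteria at each visit will be presented".

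Other categorical outputs differ by data type:

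- **Laboratory (5.5.7.2).** A shift table compares low, normal or high status at Baseline with the "worst value post-Baseline through Week 96".
- **ECG (5.5.7.4).** "A shift table will compare N (%) of ECG status at Baseline to the worst reported value through Week 96". The SAP does not say what the status categories are.
- **Vital signs (5.5.7.3) and ECHO (5.5.7.5).** No shift table. For ECHO, the rest of the plan is: "The actual value and change from Baseline to each on-treatment time point will be summarized for each ECHO parameter".

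SAP 5.4.6 defines a treatment-emergent laboratory abnormality as "any laboratory abnormality (as defined in section 5.5.7.2) that occurs following the initiation of eteplirsen which was not present at Baseline". A footnote to Table 3-2 reads "TEMA = treatment-emergent markedly abnormal". No planned table is said to use either.

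**The concern.** An incidence needs each subject counted once over a defined period, usually among those free of the condition at the start. A by-visit table gives prevalence at each visit. The same rows arise whether one subject is flagged throughout or a different subject each time. Where the criterion is an absolute limit, such as LVEF below 55%, the rows also mix abnormalities present at Baseline with those arising on treatment. That matters in advanced disease, where the protocol's background (5.1) describes progressive weakening of cardiac muscle during adolescence.

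At stake is whether a reader of the planned tables can say how many of about 20 subjects newly crossed one of the SAP's thresholds. The SAP has the right idea in 5.4.6 and in its once-per-subject AE counts (5.5.7.1), but does not carry it into these tables.

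**Working it through.** The documents give no figure to reproduce: there is no formal sample size calculation and no target incidence. The check is a comparison of planned outputs, a count of criteria, and bounds.

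**1. Outputs by data type**

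| Data type | Parameters with a criterion | Count by SAP criteria | Baseline-to-worst output |
|---|---|---|---|
| Vital signs | 4 (Table 4) | by visit | none |
| ECHO | 2 (Table 6) | by visit | none |
| ECG | 3 (Table 5; heart rate has no criterion) | by visit | shift of an undefined status |
| Laboratory | 32 rows (Tables 3-1 to 3-3) | by visit | shift of low/normal/high |

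**2. What the laboratory shift table already covers**

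Rows: 10 hematology + 20 chemistry + 2 urinalysis = 32. Total cholesterol, triglycerides and total protein are not in the panel in Protocol 10.3.3, leaving 32 − 3 = 29. This is not the whole panel: amylase, CRP and the coagulation tests, for example, are collected but have no criteria row.

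A low/normal/high shift counts a criterion if that criterion is the reference limit itself. This assumes that the worst value is taken in the direction of the criterion.

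- Fully covered, 9: hematocrit, hemoglobin, red cells, basophils, lymphocytes, monocytes, uric acid, cystatin C, KIM-1.
- Partly covered, 4: white cells, eosinophils, GGT, albumin.
- Not covered, up to 16: glucose, BUN, creatinine, sodium, chloride, calcium, AST, ALT, alkaline phosphatase, bilirubin, LDH, CK, platelets, neutrophils, potassium, urine protein.

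Check: 9 + 4 + 16 = 29.

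The 16 are of two kinds. For nine (glucose, BUN, sodium, chloride, calcium, AST, ALT, LDH, CK) the criterion is relative to Baseline, so every case at a visit is new by construction and only the cumulative count is missing. For the other 16 − 9 = 7, an absolute limit can already be met at Baseline.

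Two qualifications apply:

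- Platelets, neutrophils and potassium could be partly covered at best, if a fixed cut-off coincides with a laboratory limit. Each also has a part that is a change or a multiple of the upper limit. Urine protein depends on the same coincidence. The documents do not give the limits.
- Glucose, sodium, chloride and calcium have entries only in the predefined-change columns. If those are not criteria, the uncovered count is 16 − 4 = 12, out of 29 − 4 = 25.

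**3. What by-visit counts determine**

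If c(v) of 20 subjects are flagged at visit v, the number ever flagged lies between the largest c(v) and the smaller of 20 and the sum of the c(v). With m flagged at each of V visits, that is m to min(20, mV). The visits V come from the schedule through Week 96; the values of m are assumed.

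| Data type | V | m = 1 | m = 2 |
|---|---|---|---|
| Laboratory (Weeks 4, 8, 12, 24, 36, 48, 72, 96) | 8 | 1–8 (5–40%) | 2–16 (10–80%) |
| ECG, ECHO (Weeks 12, 24, 36, 48, 72, 96) | 6 | 1–6 (5–30%) | 2–12 (10–60%) |
| Vital signs (every 4 weeks, Weeks 4 to 96) | 24 | 1–20 (5–100%) | 2–20 (10–100%) |

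If no visit, or only one, has a flagged subject, the bounds meet and nothing is lost.

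**4. Baseline and new cases mixed**

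Assume 4 of 20 meet an absolute limit at Baseline and 5 of 20 at a later visit. The new cases number at least 5 − 4 = 1, if all four persist, and at most 5, if all four resolve. Among the 20 − 4 = 16 at risk, that is 1/16 = 6.25% to 5/16 = 31.25%.

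**The case against.** The strongest reply is that the study is single-arm and descriptive with about 20 subjects, every value is listed, and ever-counts can be worked out from the listings. Test abnormalities that alter care are AEs (Protocol 11.2.1), counted once per subject (SAP 5.5.7.1). The special-interest summaries in 5.5.7.1.1 add renal, hepatic, cytopenia, hypotension and cardiac groupings. All of this stands and limits the severity. It does not close the gap, because abnormalities that did not change care need never reach the AE tables, yet they fall within the stated endpoint.

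Four stronger readings are tempting and are not supported.

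- *The SAP gives no ever- or newly-abnormal laboratory count.* The shift table gives one by reference range through Week 96, including for sodium, potassium, AST and ALT. Protocol 10.3.3 flags values by reference range, so this output does report laboratory abnormalities. Only the SAP's added thresholds lack a cumulative count.
- *ECG has nothing.* Protocol 13.8.2.4 foresaw shift tables of predefined ECG abnormalities, and the SAP's shift table may be meant as that. The defect is the undefined status.
- *The SAP breaks the protocol without declaring it.* Protocol 13.8.2.2 to 13.8.2.4 plan frequency tables of predefined abnormalities without saying by visit or cumulative, so by-visit tables are one permissible reading. For ECHO the protocol plans only values and change in ejection fraction, and the SAP adds to that.
- *The Week 96 cut discards the extension.* The by-visit tables are not cut there, and Week 96 ends the planned treatment period.

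**Conclusion.** The point holds for the SAP's own thresholds. Followed as written, the plan reports prevalence by visit, not the incidence that the endpoints name. The gap is complete for the 4 vital-sign and 2 ECHO parameters. It is open for the 3 ECG parameters until the status is defined. For laboratory tests it concerns up to 16 of 29 collected tests with a criteria row, plus parts of 4 more; for nine of the 16, only accumulation over visits is missing.

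Severity is minor to moderate. The gap lies in planned outputs, not in data. The classification assumes that laboratory limits do not coincide with the SAP's fixed cut-offs and that the predefined-change columns are criteria. The percentage ranges rest on assumed counts and are illustrations; the 5–100% range for vital signs is not a forecast.

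**What to change.** 1. In each markedly abnormal table, for collected parameters, add a once-per-subject row: number and percent meeting the criterion at any post-Baseline assessment, including unscheduled and extension values.
2. State one end window for all data types. An example is 28 days after last dose, as for TEAEs. Add it to the laboratory definition in 5.4.6, which has no end, and label the laboratory rows with that definition.
3. For criteria with an absolute limit, use as denominator the subjects not meeting it at Baseline, and show separately those who already met it. For criteria based only on change from Baseline, use all subjects with a Baseline and at least one post-Baseline value; a row for those already abnormal would have no meaning. Where a parameter has both kinds, count each under its own rule. The QTcF screening line in Table 5 is a Baseline condition and needs no new row.
4. Say whether the predefined-change columns of Table 3-2 are criteria.
5. Define the ECG status categories by the Table 5 criteria.
6. Keep the by-visit tables as supportive. Extending the laboratory and ECG shift tables past Week 96 is optional.

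The cost is SAP wording, a few extra rows per table and modest programming for 29 + 4 + 3 + 2 = 38 parameters. No new data are needed. The three chemistry tests outside the protocol panel get a row only if they were collected.
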